11.7 Publication Policy

All unpublished information given to LA Clinical Trials, LLC by the sponsor shall not be published or disclosed to a third party without the prior written consent of the sponsor.

The data generated by this study are considered confidential information and the property of the sponsor. This confidential information may be published only in collaboration with participating personnel from the sponsor or upon sponsor's written consent to publish the information.

13. APPENDICES

13.1 Appendix 1. COVID-19 Screening

Questions for **Screening**:

At any time during the past 14 days have you...(check yes or no for each) Yes No

Felt like you had a fever?		
Had a new or worsening cough?		
Had difficulty breathing?		
Had chills?		
Had a sore throat?		
Experienced body aches or muscle aches?		
Experienced a change in your ability to smell things?		
Experienced a change in your ability to taste things?		
Close contact with someone who is sick with suspected or confirmed COVID-19?		

Before every Visit:

Temperature: _____ Note: Fever = a temperature of 100.4° F (38° C) or greater

Questions at every reminder call and every Product Use Visit:**At any time since your last clinic visit have you...(check yes or no for each) Yes No**

Felt like you had a fever?		
Had a new or worsening cough?		
Had difficulty breathing?		
Had chills?		
Had a sore throat?		
Experienced body aches or muscle aches?		
Experienced a change in your ability to smell things?		
Experienced a change in your ability to taste things?		
Close contact with someone who is sick with suspected or confirmed COVID-19?		

13.2 Appendix 2. Nicotine Use and Subjective Effects Questionnaires

13.2.1 Nicotine use history questionnaire

1. Do you currently smoke cigarettes? Yes No (If no, exclude)
2. If yes:
 - a. Average number of cigarettes smoked per day during the past 3 months?
 - i. What brand do you smoke? menthol or tobacco flavor?
 - ii. Full flavor Medium Light Ultralight
 - iii. Filter Non filter
 - iv. Commercially rolled roll your own (exclude if roll your own)
 - v.
3. Age started smoking?
4. Maximum CPD smoked on average during any one year since started smoking?
5. Have you used any nicotine containing products other than cigarettes or e-cigarettes in the past 14 days?
 - a. No Yes (exclude if yes)
6. Number of serious quit attempts?
7. If >0:
 - a. Longest time quit smoking? Years Months Days
 - b. Methods used to quit smoking:

i. Counseling	Yes  No 
ii. Nicotine gum	Yes  No 
iii. Nicotine lozenge	Yes  No 
iv. Nicotine patch	Yes  No 
v. Nicotine inhaler	Yes  No 
vi. Nicotine nasal spray	Yes  No 
vii. Chantix	Yes  No 
viii. Zyban	Yes  No 
ix. Electronic Cigarette	Yes  No 
 - c. Did you use an electronic cigarette in your most recent attempt to quit smoking?
Yes No
8. Length of time you have used the following types of electronic cigarettes?
 - a. Cigalike: Years Months Days Never used
 - b. Cartridge/Pod type: Years Months Days Never used
 - c. Vape pen: Years Months Days Never used
 - d. Large tank: Years Months Days Never used
 - e. Mod unit: Years Months Days Never used
9. Are you currently using (within the past 7 days) any of the following types of electronic cigarettes?
 - a. Cigalike: Yes No
 - b. Cartridge/Pod type: Yes No
 - c. Vape pen: Yes No
 - d. Large tank: Yes No
 - e. Mod unit: Yes No

10. Use of other tobacco products. Have you ever used:

- a. Chewing tobacco Yes _____ No _____
- b. Pipe Yes _____ No _____
- c. Hookah Yes _____ No _____
- d. Small Cigar Yes _____ No _____
- e. Large Cigar Yes _____ No _____
- f. Snus Yes _____ No _____

13.2.2 Fagerström Test for Nicotine Dependence

1. How soon after you wake up do you smoke your first cigarette? (Check one)	Within 5 minutes  6-30 minutes  31-60 minutes  After 60 minutes 
2. Do you find it difficult to refrain from smoking in places where it is forbidden, e.g., in church, at the library, in cinema, etc.? (Check one)	Yes  No 
3. Which cigarette would you hate most to give up? (Check one)	The first one in the morning  Any others 
4. How many cigarettes/day do you smoke?	10 or less  11-20  21-30  31 or more 
5. Do you smoke more frequently during the first hours after waking than during the rest of the day?	Yes  No 
6. Do you smoke if you are so ill that you are in bed most of the day?	Yes  No 

Subject Initials _____ Date _____

13.2.3 Product liking questionnaire

Please indicate on the line below how much you liked the combustible cigarette or e-cigarette you have just used.

Not at all  A great deal

13.2.4 Urge to smoke questionnaire

How strong is your current urge to smoke your usual brand cigarette?

No Urge

Very Strong Urge

The Urge to Smoke questionnaire will be completed up to 30 seconds prior to the scheduled blood draw; however, if necessary, the blood draw will take precedence over completing the questionnaire.

13.2.5 Intent to use product again questionnaire

How likely are you to use the cigarette or e-cigarette you have just used in the future?

Definitely would not

Definitely would

13.2.6 Product Evaluation Scale

	1 Not at all	2 Very Little	3 A little	4 Moderately	5 A lot	6 Quite a lot	7 Extremely
1. Was it satisfying?							
2. Did it taste good?							
3. Did you enjoy the sensations in your mouth?							
4. Did it calm you down?							
5. Did it make you feel more awake?							
6. Did it make you feel less irritable?							
7. Did it help you concentrate?							
8. Did it reduce your hunger for food?							
9. Did it make you dizzy?							
10. Did it make you nauseous?							
11. Did it immediately relieve your craving for a cigarette?							
12. Did you enjoy it?							
13. Did it relieve withdrawal symptoms?							
14. Did it relieve the urge to smoke?							
15. Was it enough nicotine?							
16. Was it too much nicotine?							
17. Was it easy to use?							
18. Were there bothersome side effects?							
19. Were you comfortable using the product in public?							
20. Did you still have a craving for a cigarette after using the product?							
21. Are you concerned that you would become dependent on this product?

## REVISION HISTORY

VERSION	DATE	DESCRIPTION OF REVISIONS	REVISED BY
0	02-AUG-2021	Original Version	Not applicable

## 1. GLOSSARY OF ABBREVIATIONS AND DEFINITION OF TERMS

Abbreviation	Description
AE	Adverse event
ANOVA	Analysis of variance
AUC	Area under the baseline-adjusted nicotine concentration-versus-time curve
BMI	Body mass index
Cavg	Average plasma concentration
Cmax	Maximum plasma concentration
CRF	Case report form
CV	Coefficient of variance
CSR	Clinical study report
ECG	Electrocardiogram
eCO	Expired carbon monoxide
Emax	Maximum response
ENDS	Electronic nicotine delivery systems
FDA	Food and Drug Administration
FTND	Fagerström Test for Nicotine Dependence
MedDRA	Medical Dictionary for Regulatory Activities
mL	Milliliters
PES	Product Evaluation Scale
ppm	Parts per million
PK	Pharmacokinetic(s)
PMTA	Premarket Tobacco Product Applications
PT	Preferred Term
SAE	Serious adverse event
SAP	Statistical analysis plan
SD	Standard deviation
SOC	System Organ Class
TFL	Tables, figures, and listings
Tmax	Time of maximum plasma concentration
TEmax	Time to maximum response
US	United States
VAS	Visual analog scale

## **2. INTRODUCTION TO THE STATISTICAL ANALYSIS PLAN**

This statistical analysis plan (SAP) is based on Study Fontem-PK-01 ‘Nicotine uptake and abuse liability assessments of 5 blu disposable electronic cigarettes in comparison to a combustible cigarette,’ original version, dated 13 July 2021. It details the methodology to be used in analyzing the data and outlines the specifications in the Tables, Figures, and Listings (TFLs) for data to be included for executing the final statistical analyses for this study.

The analyses specified in this document supersede the high-level analysis plan described in the protocol. Study measurements and assessments, planned statistical methods, and critical derived variables are summarized in this plan. Planned tables, figures and listings are specified.

The final pharmacokinetic (PK) and statistical analysis will proceed according to the SAP approved by Fontem US LLC as well as Xyzagen Inc. and CPAN Inc. Any deviations in final analyses from this SAP will be documented in the clinical study report (CSR).

## **3. INTRODUCTION TO THE STUDY**

### **3.1. BACKGROUND AND RATIONALE OF STUDY**

Fontem US LLC is undertaking clinical studies to evaluate electronic nicotine delivery systems (ENDS) to provide an alternative to combustible cigarettes for smokers. Upon user inhalation, an e-liquid solution containing nicotine, glycerol, propylene glycol, and flavor agents is heated and delivered into the lungs via an aerosol.

The objective of ENDS products is to provide sufficiently satisfying alternatives to cigarette smoking. According to the National Academies of Sciences, Engineering, and Medicine, “There is conclusive evidence that completely substituting e-cigarettes for combustible tobacco cigarettes reduces users’ exposure to numerous toxicants and carcinogens present in combustible tobacco cigarettes.”

This study is being conducted to assess the abuse liability and puffing topography of blu disposable e-cigarettes in adult combustible cigarette smokers. Nicotine uptake, subjective effects, and puff topography will be evaluated and compared with subjects’ usual brand combustible cigarette. It is anticipated that the results from this study will provide evidence that the blu disposable e-cigarettes relative to subjects’ usual brand combustible cigarettes are appropriate for the protection of the public health, and will therefore support a Premarket Tobacco Product Application (PMTA) submission to the Center for Tobacco Products at the Food and Drug Administration (FDA). The FDA’s PMTA guidance for ENDS (FDA 2019) suggests that applicants include, in addition to other information, results from studies addressing topography and use patterns and an assessment of abuse liability.

Statistical Analysis Plan  
Protocol No.: Fontem-PK-01

### **3.2. STUDY OBJECTIVES**

#### **3.2.1. Primary Objectives**

- To determine the PK of nicotine absorption into the blood of subjects when they use the blu disposable e-cigarette with varying flavors in each study arm compared to when they smoke a combustible cigarette.
- To characterize subjective effects after use of the study products and a combustible cigarette.

#### **3.2.2. Secondary Objectives**

- To compare puff topography when subjects smoke a combustible cigarette versus use of the blu disposable e-cigarette.
- To evaluate overall safety in subjects using the blu disposable e-cigarette.

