9.14.4 Puff Topography

Puff topography will be evaluated in the second product use session at Visits 2 to 7. Subjects will engage in a 1 hour *ad libitum* product use session with either their usual brand cigarette or the assigned blu disposable e-cigarette, both of which will be used with the CReSS Pocket topography device.

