10.3.3 Puff Topography

The following topography parameters will be assessed:

- Puff duration
- Puff volume
- Peak puff flow rate
- Average puff flow rate
- Inter-puff interval

Summary statistics of puff topography parameters will be presented, including means, SD, medians, and ranges.

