#### **3.3.2. Secondary Endpoints**

- Puff topography (e.g., count, duration, volume, flow rate, and inter-puff interval)

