## 8.8. PUFF TOPOGRAPHY

Puff duration, volume, peak flow, and average flow rate will be summarized by study product.

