## 8.9. PHARMACOKINETIC ANALYSIS OF NICOTINE PLASMA CONCENTRATION

PK parameters of plasma nicotine levels will be calculated using noncompartmental methods with the Phoenix WinNonlin version 8.3 software platform (Certara, Princeton, NJ). Plasma concentrations and the computed plasma PK parameters will be listed for each study product and subject.

The following PK parameters will be calculated; all parameters will be baseline-adjusted using the value at time -5 minutes:

- $C_{max,0-120}$  = Maximum plasma concentration during defined use session
- $T_{max,0-120}$  = Time of maximum plasma concentration during defined use session
- $AUC_{0-120}$  = Area under the plasma concentration-time curve from time 0 to 120 minutes during defined use session
- $C_{avg,0-120}$  = Average concentration from 0 to 120 minutes defined as  $AUC_{0-120}/120$  minutes
- $C_{max,120-180}$  = Maximum plasma concentration during the *ad libitum* puffing session
- $T_{max,120-180}$  = Time of maximum plasma concentration during the *ad libitum* puffing session
- $AUC_{120-180}$  = Area under the plasma concentration-time curve from time 120 minutes to 180 minutes during the *ad libitum* puffing session
- $C_{avg,120-180}$  = Average concentration from 120 to 180 minutes defined as  $AUC_{120-180}/60$  minutes
- $AUC_{0-180}$  = Area under the plasma concentration-time curve from time 0 minutes to 180 minutes during both puffing sessions
- $RC_{max}$  = Ratio of  $C_{max,120-180}/C_{max,0-120}$
- $RC_{avg}$  = Ratio of  $C_{avg,120-180}/C_{avg,0-120}$

A one-way or repeated measures analysis of variance will be conducted on the Outcomes Population  $C_{max,0-120}$  and  $AUC_{0-120}$  to assess for statistical differences between the Usual Brand combustible cigarette and the blu disposable e-cigarettes. Significance based on a Dunnett's multiple comparison assessment will be reported.

Statistical Analysis Plan  
Protocol No.: Fontem-PK-01

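### The objective to compare puff topography with the cigarette has no planned contrast or interval, and ad libitum nicotine exposure is only described side by side

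*SAP*

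**What the plan says.** The objectives and the rationale use comparative language. SAP 3.2.2 (and Protocol 2.1) sets the first secondary objective as "To compare puff topography when subjects smoke a combustible cigarette versus use of the blu disposable e-cigarette". SAP 3.1 adds: "Nicotine uptake, subjective effects, and puff topography will be evaluated and compared with subjects’ usual brand combustible cigarette". The primary PK objective in SAP 3.2.1 concerns e-cigarettes "with varying flavors in each study arm compared to when they smoke a combustible cigarette" and names no session. By contrast, the second primary objective, on subjective effects, asks only to characterize.

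On measurement, Protocol 9.14.4 states: "Puff topography will be evaluated in the second product use session at Visits 2 to 7". That is the ad libitum hour; no topography is taken in the defined session.

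On analysis, SAP 8.8 reads in full: "Puff duration, volume, peak flow, and average flow rate will be summarized by study product". Protocol 10.3.3 says: "Summary statistics of puff topography parameters will be presented, including means, SD, medians, and ranges". The one formal comparison in either document is in SAP 8.9 (and Protocol 10.3.1): an analysis of variance on Cmax,0-120 and AUC0-120, with Dunnett's procedure, "to assess for statistical differences between the Usual Brand combustible cigarette and the blu disposable e-cigarettes". The text leaves open whether it is one-way or repeated-measures. The other PK parameters are listed and summarized by product. SAP 9 records no changes to the planned analyses.

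**The concern.** An objective worded as a comparison needs an estimate of the difference and a measure of its uncertainty. For topography there is neither, and since it is measured in no other session, nothing elsewhere in the plan supplies them. For nicotine PK the formal comparison stops at 120 minutes, so the hour in which subjects choose how much to use is described but not contrasted.

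The design has each completer use all six products, so the relevant precision is within-subject. Separate means and SDs leave that out. The study is meant to support a PMTA submission, and both documents cite guidance asking for results on topography and use patterns. A reader of the report would have six columns of summaries and no stated precision for any e-cigarette-versus-cigarette difference in free use.

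**Working it through.** **1. Coverage of the PK parameters.** SAP 8.9 lists 11 parameters. Two are tested against the cigarette, both from 0-120 minutes. Seven use ad libitum data: Cmax, Tmax, AUC and Cavg for 120-180, AUC0-180, and the two ratios. None of the seven has a planned contrast with the cigarette. Seven overstates the distinct information, however. Cavg,120-180 is AUC120-180 divided by 60, AUC0-180 contains the window already tested, and each ratio compares two sessions within one product. The main ad libitum exposure measures without a contrast are Cmax,120-180 and AUC120-180.

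**2. Coverage of topography.** The endpoint in SAP 3.3.2 names, as examples, count, duration, volume, flow rate and inter-puff interval. SAP 8.8 summarizes duration, volume, peak flow and average flow. Protocol 10.3.3 adds inter-puff interval. Puff count is in neither analysis list, and inter-puff interval is missing from the SAP's. No topography measure has a contrast.

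**3. What the planned summaries can show.** With the same subjects on two products, the difference between the product means equals the mean within-subject difference, so its size can be read from the tables. Its standard error cannot, because it depends on the within-subject correlation, which by-product SDs do not contain. If subjects drop out, the reduced denominators in SAP 7.3.1 mean that the two columns cover different subjects, and the equality no longer holds exactly.

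**4. Precision.** The plan has no figure to reproduce: SAP 6 states that no power calculation was done and gives no SD. In units of the SD of the within-subject difference, a paired 95% interval with 20 completers has half-width t(19)/√20 = 2.093/4.472 = 0.47.

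To put this on a ratio scale, variances must be assumed. Take log-scale between-subject SD sb = 0.4 to 0.6, within-subject SD sw = 0.3 to 0.5 and n = 20. None of these SDs is in the documents.

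- Paired: SE = √(2·sw²/20), with t on 5 × 19 = 95 df (1.985).
  - sw = 0.3: SE 0.0949, limits ×/÷ exp(0.188) = 1.21.
  - sw = 0.5: SE 0.1581, limits ×/÷ exp(0.314) = 1.37.
- From separate means and SDs: SE = √(2·(sb² + sw²)/20), with t on 38 df (2.024).
  - sb = 0.4, sw = 0.3: SE 0.1581, limits ×/÷ exp(0.320) = 1.38.
  - sb = 0.6, sw = 0.5: SE 0.2470, limits ×/÷ exp(0.500) = 1.65.
- Ratio of log-scale widths, unpaired to paired:
  - smallest, at sb = 0.4, sw = 0.5: 0.410/0.314 = 1.31.
  - largest, at sb = 0.6, sw = 0.3: 0.429/0.188 = 2.28.

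The unpaired interval is not a planned output. It represents what a reader could work out from the by-product tables alone.

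**The case against.** The strongest reply is that the plan does compare, descriptively. The cigarette is Product F, so every by-product table sets it beside the five e-cigarettes. Protocol 10.3.1 plots mean nicotine for each product with 95% confidence intervals at each time point, and sampling runs to 180 minutes. Listings by subject preserve the pairing, so a paired difference and its standard error could be rebuilt. This stands as far as it goes: the information is not lost, and the size of a difference is visible. But the plotted intervals are for each mean, not for a difference, and a calculation rebuilt from listings is not a planned analysis.

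A second reply is that confining inference to two parameters is reasonable restraint in a Phase I study with no power calculation, and that Protocol 1.1 itself frames delivery relative to cigarettes as Cmax after acute use. That is a fair reason not to add significance tests. It is not a reason to leave out intervals, and it does not touch topography, which has no defined-session counterpart.

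A third reply is that the cigarette is always smoked at Visit 2 while only Visits 3 to 7 are randomized (SAP 4.1), so any such contrast mixes product with visit order. This is true, and it applies equally to the analysis of variance already planned. It has to be stated as a limit.

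A reader might go further and infer that nothing in the ad libitum hour is compared, that the primary PK objective is unanswered, or that the trial cannot say how far products differ. The documents do not support these readings. The PK objective is formally tested in the defined session, and the ad libitum results are shown next to the cigarette. Nor does either document rank the ad libitum hour above the defined session for abuse liability.

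**Conclusion.** The concern holds in a limited form. The topography objective promises a comparison and has no planned contrast or interval for a difference. Ad libitum nicotine exposure is described side by side with the cigarette, without a contrast, while the primary PK objective is formally tested for the defined session only. What is missing is within-subject precision, not the size of the difference. This conclusion rests on the text and needs no assumption. The figures of ×/÷ 1.21 to 1.37 paired and ×/÷ 1.38 to 1.65 unpaired are illustrations. They depend on the assumed SDs, on 20 complete subjects and, for the paired limits, on an error variance common to all products. The topography gap should be corrected; the PK addition is supportive.

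**What to change.** **SAP 8.8.** Fit a within-subject model with product as a fixed effect and subject as a random effect. Specify the repeated-measures form explicitly and rule out the one-way option, which would ignore the pairing. Apply it to the per-subject session mean of puff duration, volume, peak flow, average flow and inter-puff interval, and to the session total for puff count. Add count and inter-puff interval to the summaries as well. Report each e-cigarette versus the cigarette as a ratio or difference with a 95% CI, and fix the scale for each measure in advance.

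**SAP 8.9.** Do the same, as supportive estimation, for Cmax,120-180 and AUC120-180, and optionally for AUC0-180.

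**Both sections.** Label the results as estimates with no significance claim, and state that the cigarette's fixed place at Visit 2 confounds product with visit order. If the sponsor does not want a contrast, the consistent alternative is to reword the topography objective as description.

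The cost is SAP wording and a few tables from data already collected, with no change to study conduct. The downside is more intervals without multiplicity adjustment, which the labelling makes plain.

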### **3.3. STUDY ENDPOINTS**

#### **3.3.1. Primary Endpoints**

- Baseline-adjusted plasma nicotine  $C_{max,0-120}$ ,  $C_{avg,0-120}$ ,  $T_{max,0-120}$ ,  $AUC_{0-120}$ ,  $C_{max,120-180}$ ,  $T_{max,120-180}$ ,  $AUC_{120-180}$ ,  $C_{avg,120-180}$ ,  $AUC_{0-180}$
- Subjective effects measures:
  - Product liking assessment
  - Intent to Use Product Again assessment
  - Urge to Smoke Questionnaire
  - Product Evaluation Scale (PES)
- Mass change of blu disposable e-cigarette during puffing

#### **3.3.2. Secondary Endpoints**

- Puff topography (e.g., count, duration, volume, flow rate, and inter-puff interval)

#### **3.3.3. Safety Endpoints**

- Heart rate and blood pressure during product use sessions
- Adverse events (AE)/Serious adverse events (SAE)

### **3.4. STUDY DESIGN**

This will be a part-randomized, open-label abuse liability assessment and puffing topography study of nicotine-containing products carried out in 20 healthy adult volunteers who smoke combustible cigarettes. The schedule of events is presented in Section 10.

Statistical Analysis Plan  
Protocol No.: Fontem-PK-01

After screening, subjects will attend the study site 6 times (Visits 2-7). Prior to each visit, subjects will be required to refrain from using any nicotine-containing products for a period of at least 12 hours before study product use.

During their second visit (Visit 2), the subjects will smoke their usual brand cigarette during 2 use sessions. In the first session, subjects will smoke a single combustible cigarette of their usual brand by taking 10 puffs, 30 seconds apart. Blood samples (5 mL) will be obtained for plasma nicotine analysis at -5, 3, 5, 7, 10, 15, 20, 30, 45, 60, 90, and 120 minutes relative to the first puff on the cigarette. Blood pressure and heart rate will be recorded at -10 (baseline), 8, 60, and 120 minutes. Subjects will be asked to complete several subjective effects questionnaires at various points either before, during, or after product use.

In the second session, which will begin immediately after the 120 minute blood draw and after all questionnaires have been completed, subjects will be allowed to take *ad libitum* puffs on their usual brand cigarette for a period of 60 minutes (1 hour) while puffing topography measurements are made with a CReSS Pocket device. Subjects may use as many cigarettes as they like. Blood samples for nicotine PK analysis will be drawn at 135, 150, 165, and 180 minutes relative to the first puff on the cigarette at the visit (i.e., at 15, 30, 45, and 60 minutes of the *ad lib* session). Blood pressure and heart rate will be recorded at 180 minutes. Subjective effects questionnaires will also be completed at specified time points.

At the end of Visit 2, subjects will be randomized into a product use sequence for testing the investigational products (blu disposable e-cigarettes).

Subjects will then visit the study site on 5 subsequent occasions (Visits 3-7); at each visit, the subjects will use their assigned blu disposable e-cigarette during 2 use sessions (standardized and *ad lib*, same as at Visit 2). Study procedures during the 2 use sessions will be the same as at Visit 2.

All blu disposable e-cigarettes (Table 1) will be provided by the sponsor. At Visit 2, subjects will smoke their own brand of combustible cigarette.

